8.3.1.1. Reporting SAEs to Pfizer Safety

All SAEs occurring in a participant during the active collection period are reported to Pfizer Safety on the Clinical Trial (CT) SAE Report Form immediately and under no circumstance should this exceed 24 hours, as indicated in [Appendix 3](#). The investigator will submit any updated SAE data to the sponsor within 24 hours of it being available.

All SAEs occurring in a participant during the active collection period are reported to Pfizer Safety on the CT SAE Report Form.

SAEs occurring in a participant after the active collection period has ended are reported to Pfizer Safety if the investigator becomes aware of them; at a minimum, all SAEs that the investigator believes have at least a reasonable possibility of being related to IP must be reported to Pfizer Safety.

8.3.1.2. Recording Non-serious AEs and SAEs on the CRF

During the active collection period, both non-serious AEs and SAEs are recorded on the CRF.

8.3.2. Method of Detecting AEs and SAEs

The method of recording, evaluating, and assessing causality of AE and SAE and the procedures for completing and transmitting SAE reports are provided in [Appendix 3](#).

Care will be taken not to introduce bias when detecting AEs and/or SAEs. Open-ended and non-leading verbal questioning of the participant is the preferred method to inquire about AE occurrences.

8.3.3. Follow-up of AEs and SAEs

After the initial AE/SAE report, the investigator is required to proactively follow each participant at subsequent visits/contacts. For each event, the investigator must pursue and obtain adequate information until resolution, stabilization, the event is otherwise explained, or the participant is lost to follow-up (as defined in [Section 7.3](#)).

In general, follow-up information will include a description of the event in sufficient detail to allow for a complete medical assessment of the case and independent determination of possible causality. Any information relevant to the event, such as concomitant medications and illnesses, must be provided. In the case of a participant death, a summary of available autopsy findings must be submitted as soon as possible to Pfizer Safety.

Further information on follow-up procedures is given in [Appendix 3](#).

8.3.4. Regulatory Reporting Requirements for SAEs

- Prompt notification by the investigator to the sponsor of a SAE is essential so that legal obligations and ethical responsibilities towards the safety of participants and the safety of a study intervention under clinical investigation are met.
- The sponsor has a legal responsibility to notify both the local regulatory authority and other regulatory agencies about the safety of a study intervention under clinical investigation. The sponsor will comply with country-specific regulatory requirements relating to safety reporting to the regulatory authority, Institutional Review Boards (IRB)/Independent Ethics Committees (IEC), and investigators.
- Investigator safety reports must be prepared for suspected unexpected serious adverse reactions (SUSAR) according to local regulatory requirements and sponsor policy and forwarded to investigators as necessary.
- An investigator who receives an investigator safety report describing a SAE or other specific safety information (eg, summary or listing of SAEs) from the sponsor will review and then file it along with the Investigator's Brochure and will notify the IRB/IEC, if appropriate according to local requirements.

8.3.5. Exposure During Pregnancy or Breastfeeding, and Occupational Exposure

Exposure to the IP under study during pregnancy or breastfeeding and occupational exposure are reportable to Pfizer Safety within 24 hours of investigator awareness.

8.3.5.1. Exposure During Pregnancy

- Details of all pregnancies in female participants, female partners of male participants, female family members, and healthcare providers who have been exposed to study intervention will be collected after the start of study intervention and until the end of the active collection period.

- If a pregnancy is reported, the investigator should inform the sponsor within 24 hours of learning of the pregnancy and should follow the procedures outlined in [Appendix 4](#).
- Abnormal pregnancy outcomes (eg, spontaneous abortion, fetal death, stillbirth, congenital anomalies, ectopic pregnancy) are considered SAEs.

8.3.5.2. Exposure During Breastfeeding

Scenarios of exposure during breastfeeding must be reported, irrespective of the presence of an associated SAE, to Pfizer Safety within 24 hours of the investigator's awareness, using the CT SAE Report Form. An exposure during breastfeeding report is not created when a Pfizer drug specifically approved for use in breastfeeding women (eg, vitamins) is administered in accord with authorized use. However, if the infant experiences an SAE associated with such a drug's administration, the SAE is reported together with the exposure during breastfeeding.

8.3.5.3. Occupational Exposure

An occupational exposure occurs when, during the performance of job duties, a person (whether a healthcare professional or otherwise) gets in unplanned direct contact with the product, which may or may not lead to the occurrence of an AE.

An occupational exposure is reported to Pfizer Safety within 24 hours of the investigator's awareness, using the CT SAE Report Form, regardless of whether there is an associated SAE. Since the information does not pertain to a participant enrolled in the study, the information is not recorded on a CRF; however, a copy of the completed CT SAE Report Form is maintained in the investigator site file.

8.3.6. Disease-Related Events and/or Disease-Related Outcomes Not Qualifying as AEs

The following disease related events are common in participants with AD:

- AD
- Eczema
- Flare of AD

Because these events are expected in this remitting and relapsing disease, they will not be reported as AEs. These events should be documented and recorded on the appropriate CRF as occurrence of a flare of AD during the maintenance period represents the efficacy outcome measure.

NOTE: However, if either of the following conditions applies, then the event must be recorded and reported as an AE:

- In the investigator's opinion, the event is of greater intensity or severity than the individual participant's condition at baseline (Day 1 of the run-in period).

OR

- The investigator considers that there is a reasonable possibility that the event was related to study intervention.

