2.3. Benefit/Risk Assessment

This study will evaluate crisaborole at a dose strength and regimen that has been demonstrated to be well tolerated and efficacious based on the completed clinical development program data.

The crisaborole dose strength and regimen (2% BID) of crisaborole for this study has been shown to have a favorable safety profile and to be well tolerated in participants 3 months of age and older who participated in previously conducted studies. Crisaborole ointment, 2% BID regimen was studied in two Phase 3, randomized, double-blind, vehicle-controlled studies in participants 2 years of age and older (AN2728-AD-301 and AN2728-AD-302), a Phase 3 open-label long-term safety study in participants 2 years of age and older (AN2728-AD-303) up to 48 weeks, and a Phase 4 open-label safety study in participants 3 to <24 months of age (C3291002).

Data from the 2 controlled studies (AN2728-AD-301 and AN2728-AD-302) showed no systemic safety concerns in participants aged 2 years and older. The safety profile from the open-label long-term clinical study (AN2728-AD-303) was consistent with that of the 2 controlled pivotal clinical studies with no new clinically important safety signals identified. The safety profile observed in the Phase 4 open-label study in participants 3 to <24 months of age (C3291002) was consistent with previous studies in participants 2 years of age and older with no new clinically important safety signals identified.

The most common drug-related AEs from the 2 controlled studies were application site reactions (5.6% and 3.6% for crisaborole and vehicle groups, respectively) and most were classified as mild. Of these drug-related application site reactions, application site pain (eg, burning or stinging) was the only treatment-related AE that showed a clinically relevant difference in rates between the treatment groups (4.4% and 1.2% for crisaborole and vehicle groups, respectively). Generally, application site pain was noted early in the treatment period and was transient in nature, resolving spontaneously.

A review of the post marketing safety data, to date, has shown that the type and occurrence of adverse event reports are consistent with the known safety profile of crisaborole. No new safety signals or unusual trends have been identified.

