3. OBJECTIVES, ESTIMANDS AND ENDPOINTS

Objectives	Endpoints
Primary	

Efficacy: To evaluate the long-term efficacy of crisaborole ointment, 2%, QD for maintenance therapy and flare reduction in pediatric and adult participants ≥ 3 months of age with mild-to-moderate AD who responded to crisaborole ointment, 2%, BID treatment.	
Flare-free maintenance until onset of first flare during the 52-week double-blind period

Safety: To evaluate the safety and local tolerability of crisaborole ointment, 2%, QD for maintenance therapy and flare reduction in pediatric and adult participants ≥ 3 months of age with mild-to-moderate AD	
Incidence of treatment emergent adverse events
Secondary	

To evaluate other long-term efficacy parameters for maintenance therapy and flare reduction of crisaborole ointment, 2%, QD in pediatric and adult participants ≥ 3 months of age	Key secondary endpoints during the 52-week double-blind period: 
Number of flare-free daysNumber of flares

with mild-to-moderate AD who responded to crisaborole ointment, 2%, BID treatment
	
 • Pruritus response maintenance until onset of first flare 
Other secondary endpoints during the 52-week double-blind period:
 
 • $\geq 50\%$ reduction in Eczema Area and Severity Index (EASI)50 response maintenance • Maintenance of Dermatology Quality of Life Assessments • Maintenance of Patient Oriented Eczema Measure (POEM) 
The following will be assessed during flare treatment period:
 
 • Severity of flare on Investigator’s Static Global Assessment (ISGA) and EASI • Duration of flare episode

Additional Secondary
	

 • To evaluate the long-term efficacy of crisaborole ointment, 2%, QD for maintenance therapy and flare reduction in participants ≥ 3 months of age with mild-to-moderate AD 	
The following will be assessed as change from baseline of each respective treatment period (run-in, double-blind, and flare treatment):
 
 • EASI scores • ISGA scores • Treatable AD %BSA • Most commonly affected AD %BSA

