9.4.2. Safety Analyses

All safety analyses will be performed on the Safety Population.

Endpoint	Statistical Analysis Methods
Primary	
AEs, SAEs, local tolerability, discontinuations, and clinically significant changes in vital signs will be descriptively summarized and will be presented in tabular and/or graphical format by open-label run-in period, flare treatment period in the maintenance period, and QD period. No imputation will be made for missing safety data.

CCI

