6.7.1. Adverse Events

The safety data will be summarized separately by period: OL period for SAF-OL, DB QD period for SAF-DB, and flare treatment period for SAF-DB in accordance with Pfizer Data Standards. All safety data will be summarized descriptively through appropriate data tabulations, descriptive statistics, categorical summaries, and graphical presentations. The safety data will be summarized for overall events and treatment area events. Safety endpoints for the study include:

- Incidence of TEAEs.
- Incidence of SAEs and AEs leading to discontinuation.

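### The SAP's undefined treatment-area count does not separate flare-type AEs from local reactions, so the pooled contrast shifts towards crisaborole by an unknown amount

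*Protocol*

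**What the plan says.** Local tolerability is part of the primary safety objective (Protocol Section 3): "To evaluate the safety and local tolerability of crisaborole ointment, 2%, QD". Protocol 9.4.2 lists it as an item of its own: "AEs, SAEs, local tolerability, discontinuations, and clinically significant changes in vital signs will be descriptively summarized".

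For AD, eczema and flare, Protocol 8.3.6 sets a default: "Because these events are expected in this remitting and relapsing disease, they will not be reported as AEs". Either of two conditions reverses it. One is that, in the investigator's opinion, "the event is of greater intensity or severity than the individual" participant's condition on run-in Day 1. The other is: "The investigator considers that there is a reasonable possibility that the event was related to study intervention". The first applies whatever the causality judgement.

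The SAP names no local-tolerability endpoint in 3.6.1 and no analysis under that name in 6.7. Its one local summary is a sentence in 6.7.1: "The safety data will be summarized for overall events and treatment area events". The SAP does not say what makes an event a treatment area event, or whether AD terms belong there. It does expect AD worsening in the AE data: 6.1.2 finds it by preferred term, and 6.2.2 refers to such AEs on treated lesions. Protocol 6.1.1 requires listed and new lesions to be treated. SAP 6.7.1 tabulates the open-label, double-blind QD and flare-treatment periods separately and leaves the layout to sponsor standards.

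**The concern.** Flare is the primary efficacy event, and the trial is powered on its being more frequent on vehicle. Some flares become AEs for reasons unconnected with tolerability, and they arise on the skin being treated. If the treatment-area count includes them, a working drug lowers its own count relative to vehicle through efficacy. A real excess of stinging, burning or other local reaction on crisaborole would then look smaller in the pooled incidence, and could disappear or reverse. Total treatment-emergent AEs are affected in the same way. Local reactions are the most common drug-related AEs that Protocol 2.3 reports for crisaborole, so this is the safety contrast where a clear reading matters most.

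**Working it through.** **Inputs from the documents**
- Protocol 9.2: 162 first flares, about 250 randomised 1:1, hazard ratio 0.556, two-sided 0.05, power about 96%.
- Protocol 2.3, the two controlled BID studies: "application site reactions (5.6% and 3.6% for crisaborole and vehicle groups, respectively"; application-site pain 4.4% and 1.2%.

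**Assumptions**
- First-flare times are exponential, with no dropout.
- A share *q* of first flares is recorded as treatment-area AEs. It is the same in both arms and independent of application-site reactions. The documents give no value for *q*; 0 to 30% is shown.

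**Step 1: the plan's power.** Φ(½√162 × |ln 0.556| − 1.96) = Φ(6.364 × 0.587 − 1.96) = Φ(1.776) = 96.2%. The stated figure is reproduced.

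**Step 2: flare rates implied by the design.** Let *H* be the vehicle cumulative hazard at Week 52. Solve ½(1 − e^−H) + ½(1 − e^−0.556H) = 162/250 = 0.648, giving *H* = 1.404.
- Vehicle: 1 − e^−1.404 = 0.754, about 94 of 125.
- Crisaborole: 1 − e^−0.780 = 0.542, about 68 of 125.
- Gap before rounding: 21.3 points.

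**Step 3: pooled incidence.** With reaction rate *r* and flare rate *p*, participant-level incidence = 1 − (1 − r)(1 − q·p). Crisaborole v vehicle, with the difference in points from unrounded values:

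| q | All application-site reactions | Application-site pain |
|---|---|---|
| 0 | 5.6% v 3.6% (+2.0) | 4.4% v 1.2% (+3.2) |
| 5% | 8.2% v 7.2% (+0.9) | 7.0% v 4.9% (+2.1) |
| 10% | 10.7% v 10.9% (−0.2) | 9.6% v 8.7% (+0.9) |
| 20% | 15.8% v 18.1% (−2.3) | 14.8% v 16.1% (−1.3) |
| 30% | 20.9% v 25.4% (−4.5) | 19.9% v 23.6% (−3.6) |

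**Step 4: break-even.** With reaction rates *c* (crisaborole) and *v* (vehicle) and flare rates *p_c* and *p_v*, the excess is zero at q = (c − v) / [(1 − v)p_v − (1 − c)p_c].
- All reactions: 0.020 / (0.964 × 0.754 − 0.944 × 0.542) = 0.020 / 0.215 = about 9%.
- Pain: 0.032 / (0.988 × 0.754 − 0.956 × 0.542) = 0.032 / 0.227 = about 14%.

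**Step 5: unequal shares.** For all reactions, the shift favours crisaborole as long as *q* on crisaborole is below about 1.4 times *q* on vehicle (0.727 / 0.512 = 1.42).

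**Step 6: scale.** At *q* = 10%, flare AEs affect about 6.8 crisaborole and 9.4 vehicle participants (0.10 × 67.7 and 0.10 × 94.3). Reactions alone would give 7.0 and 4.5. Even with no flare AEs, 125 per arm has only about 11% power for the all-reaction difference and 33% for pain. The comparison is descriptive, and a few events can move it.

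**Why *q* cannot be derived.** Run-in ISGA is 2 or 3 (Protocol 5.1) and a flare starts at ISGA 2 (4.1). On that scale, a participant who entered at 2 must reach at least 3 to be worse than run-in, and one who entered at 3 must reach 4. Many flares will not qualify. The test, however, is the investigator's opinion and not an ISGA threshold. Protocol 10.3.1 also says both that lack of efficacy in itself is not an AE and that it is one. Those two statements must be reconciled, and the second would raise *q*.

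**The case against.** **A reader might infer that the treatment-area measure counts flare AEs as a matter of plan.** The documents do not say so. The term is undefined, and the table layouts follow sponsor standards that are not in the documents. Inclusion is the natural reading, because the lesions are the treated area and no exclusion is written, but it remains an inference.

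**A reader might infer that application-site reactions would be hidden.** That is not shown. Application-site pain and the AD terms are different terms, and SAP 6.1.2 already picks out AD worsening by preferred term. If preferred terms are tabulated, the reactions stay visible. Masking is limited to the pooled incidence, although that is the only local summary the SAP names.

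**A reader might infer that even a low share of flares cancels the known risk.** The share is unknown and limited by the run-in ISGA. At 5% the excess persists on both benchmarks, and at 10% it persists for pain, the reaction Protocol 2.3 singles out as clinically relevant. The benchmark itself is also weak. It counts drug-related events under BID treatment, and Protocol 2.3 describes the pain as early and transient. Everyone randomised here has already used and responded to BID crisaborole. The rates illustrate the mechanism and do not forecast this trial.

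**The period split helps only in part.** AD AEs that start during flare treatment go to another table, and step 3 does not remove them. But BID flare treatment starts only after ISGA 2 or more is confirmed (Protocol 4.1), and SAP 6.1.2 allows reported worsening to begin before that. Such AEs fall in the QD period, which is the randomised comparison.

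**Tolerability is not wholly unassessed.** The schedule has a targeted physical examination, which includes skin, at in-clinic visits. What is missing is a dedicated tolerability scale.

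**Conclusion.** The point stands as a defect in the pooled summaries. Protocol 8.3.6 can turn treatment-unrelated flares into AEs, and the SAP's only named local summary is undefined and carries no exclusion. With more flares on vehicle, the treatment-area and total AE contrasts then shift in favour of crisaborole. The direction rests on three things: that AD AEs are counted, that the drug reduces flares as designed, and that the recorded share is not much higher on crisaborole than on vehicle.

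The size cannot be stated. The break-even shares of about 9% and 14% are illustrations built on borrowed BID rates, exponential times and no dropout. No figure in the documents is wrong on this point, no efficacy result is affected, and the safety analysis has no formal test attached. The change is still worth making, because it bears on a primary safety objective and costs little.

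**What to change.** In SAP 6.7.1, define treatment area events and state whether AD, eczema and flare terms belong. For SAF-DB in the double-blind QD period, with the flare-treatment period shown separately, report by arm, counting participants:

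1. All treatment-area treatment-emergent AEs.
2. Treatment-area treatment-emergent AEs excluding AD, eczema and flare terms. Name this row, together with a separate application-site-reaction row, as the local-tolerability comparison.
3. AD, eczema and flare AEs on their own line, split by related or not related.

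Show total treatment-emergent AEs with and without the AD terms in the same way. Row 2 must be recounted from participant-level data, because one participant can have both kinds of event and preferred-term rows cannot simply be subtracted.

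The exclusion should go by term and not by causality. Protocol 10.3.3 handles an event of unknown cause as related for reporting purposes, so a causality rule could leave uncertain flares in the count.

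The cost is SAP wording, a flag derived from preferred term, and a few table rows; preferred term and causality are already collected. The drawback is that genuine drug-related AD worsening leaves row 2 and must be read from line 3, so row 1 stays beside row 2.

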8.3.7. Wearable Device Incidents

A wearable device incident is an incident associated with a study device, including any malfunction or deterioration in the characteristics and/or performance of a device as well as any inadequacy in the labeling or the instructions for use which, directly or indirectly, might lead to or might have led to the death of a participant/user/other person or to a serious deterioration in his/her state of health.

Reporting of wearable device incidents will follow AE and SAE reporting procedures.

NOTE: Incidents fulfilling the definition of an AE/SAE will also follow the processes outlined in [Section 8.3.3](#) and [Appendix 3](#) of the protocol.

8.3.8. Medication Errors

Medication errors may result from the administration or consumption of the study intervention by the wrong participant, or at the wrong time, or at the wrong dosage strength.

Exposures to the study intervention under study may occur in clinical trial settings, such as medication errors.

Safety Event	Recorded on the CRF	Reported on the CT SAE Report Form to Pfizer Safety Within 24 Hours of Awareness
Medication errors	All (regardless of whether associated with an AE)	Only if associated with an SAE

Medication errors include:

- Medication errors involving participant exposure to the study intervention;
- Potential medication errors or uses outside of what is foreseen in the protocol that do or do not involve the participating participant.

Such medication errors occurring to a study participant are to be captured on the medication error page of the CRF, which is a specific version of the AE page.

In the event of a medication dosing error, the sponsor should be notified immediately.

Whether or not the medication error is accompanied by an AE, as determined by the investigator, the medication error is recorded on the medication error page of the CRF and, if applicable, any associated AE(s), serious and non-serious, are recorded on an AE page of the CRF.

Medication errors should be reported to Pfizer Safety within 24 hours on a CT SAE Report Form **only when associated with an SAE**.

8.4. Treatment of Overdose

While overdose following topical administration is unlikely, there is a possibility that an excess of crisaborole may be applied. If too much crisaborole has been applied, the excess can be wiped off. The investigator should monitor participant for any AEs/SAEs.

8.5. Pharmacokinetics

PK parameters are not evaluated in this study.

